6. SUPPORTING DOCUMENTATION

6.1. Appendix 1 List of Abbreviations

AE	adverse event
ALT/SGPT	alanine aminotransferase
ANCOVA	analysis of covariance
AST/SGOT	aspartate aminotransferase
ATC	anatomic and therapeutic class
BMI	body mass index
CI	confidence interval
CRF	case report form
CSR	Clinical Study Report
DMC	Data Monitoring Committee
ECG	electrocardiogram
eCRF	electronic case report form
FAS	full analysis set
FDA	Food and Drug Administration
ICH	International Conference on Harmonisation
IWRS	interactive web response system
LOCF	last observation carried forward
MedDRA	Medical Dictionary for Regulatory Activities
PD	pharmacodynamic(s)
PK	pharmacokinetic(s)
SAE	serious adverse event
SAP	Statistical Analysis Plan
SD	standard deviation
SMQs	standardized MedDRA queries
TEAE	treatment-emergent adverse event
TEMA	treatment-emergent markedly abnormal
WHO	World Health Organization
WHO-DD	World Health Organization Drug Dictionary

6.2. Appendix 2 Changes to Protocol-Planned Analyses

The analysis of time to event endpoints as described in the protocol includes both descriptive analysis, log-rank test and Cox proportional hazards model. However, since time to relapse is an exploratory endpoint, the analysis of this endpoint will only be descriptive.

6.3. Appendix 3 Demographics and Baseline Characteristics

6.3.1. Demographics

The following demographic variables will be summarized by intervention group:

Continuous Variables	Summary Type
Age (years)	Descriptive statistics (N, mean, standard deviation [SD], median and range [minimum and maximum]
Weight (kg) at baseline	
Categorical Variables	
Age (18-64 years, >=65 years)	
Sex (male, female, undifferentiated)	
Japanese Ancestry (Yes, No)	
Occupational/employment status (full time employed, part time employed, casually employed, sheltered work, employed, but currently on sick or disability leave, unemployed due to depression, but seeking work, unemployed for reasons unrelated to depression, but seeking work, unemployed due to depression, but not seeking work, unemployed for reasons unrelated to depression, but not seeking work, retired, housewife or dependent husband/partner, student, no information available)	Frequency distribution with the number and percentage of participants in each category.

The following variables will be summarized for female participants by intervention group:

Continuous Variables	Summary Type	
Average length of menstrual cycle (days)	Descriptive statistics (N, mean, standard deviation	
Time from last menstrual period to date of assessment	[SD], median and range [minimum and maximum]	
Categorical Variables		
Subject's childbearing potential (of childbearing potential, permanently sterilized, postmenopausal, not applicable)	Frequency distribution with the number and percentage of participants in each category.	
Did menstrual period occur since last assessment (Yes, No)		

6.3.2. Nasal examination

The following variables will be summarized for the nasal examination performed at screening by intervention group:

Categorical Variables	Summary Type
Condition (Structural/Functional Abnormalities, Septal Deviation, Signs of Infections, Obstruction/Functional Lesions, Other Findings)	Frequency distribution with the number and percentage of participants in each category.

The specifications of the conditions recorded will be listed.

6.3.3. Psychiatric history

The following variables will be summarized for the psychiatric history performed at screening by intervention group:

Continuous Variables	Summary Type	
Subjects age in years when diagnosed with MDD (years)	Descriptive statistics (N, mean, standard deviation [SD], median and range [minimum and maximum]	
Total number of major depressive episodes to date, including current episode		
Duration of Current Episode (weeks)		
Categorical Variables		
Would the subject be eligible for electroconvulsive therapy, had he/she NOT been enrolled in this clinical trial (Yes, No)		
Does the subject have a family history of psychiatric disorders (Yes, No, Unknown)	Frequency distribution with the number and percentage of participants in each category.	
Psychiatric Disorder (Alcohol Abuse, Anxiety Disorder, Bipolar Disorder, Depression, Schizophrenia, Substance, Abuse, Other)		
Check all family members who have or had the selected psychiatric disorder (Father, Mother, Siblings, Other)		

The specified Other psychiatric disorders and Family members will be listed.

6.3.4. Mini International Neuropsychiatric Interview (MINI)

Participants will undergo the MINI (a structured diagnostic interview) to confirm the diagnosis of MDD and to determine if there are other psychiatric conditions present.

The following variables will be summarized for the MINI performed at screening by intervention group:

Categorical Variables	Summary Type
Was the questionnaire completed (Yes, No)	
Reason Not Done (Subject too ill, Subject refused, Other)	
Major depressive episode, Current (2 weeks)	
Major depressive episode, Past	
Major depressive episode, Recurrent	Frequency distribution with the number and percentage of participants in each category.
Major depressive disorder, Current (2 weeks)	
Major depressive disorder, Past	
Major depressive disorder, Recurrent	
Suicidality, Current (Past Month)	
Suicidality, Lifetime attempt	
Suicidality level (Low, Moderate, High)	

Suicide behavior disorder, Current
Suicide behavior disorder, In early remission
Manic episode, Current
Manic episode, Past
Hypomanic episode, Current
Hypomanic episode, Past
Hypomanic episode, Not Explored
Bipolar I disorder, Current
Bipolar I disorder, Past
Bipolar I disorder with psychotic features, Current
Bipolar I disorder with psychotic features, Past
Bipolar II disorder, Current
Bipolar II disorder, Past
Other specified bipolar and related disorder, Current
Other specified bipolar and related disorder, Past
Panic disorder, Current (Past Month)
Panic disorder, Lifetime
Agoraphobia, Current
Social anxiety disorder (Social Phobia), Current (Past Month)
Obsessive-compulsive disorder, Current (Past Month)
Posttraumatic stress disorder, Current (Past Month)
Alcohol use disorder, Past 12 Months
Substance use disorder (Non-alcohol), Past 12 Months
Any psychotic disorder, Current
Any psychotic disorder, Lifetime
Major depressive disorder with psychotic features, Current
Major depressive disorder with psychotic features, Past
Bipolar I disorder with psychotic features, Current
Bipolar I disorder with psychotic features, Past
Anorexia nervosa, Current (Past 3 Months)
Bulimia nervosa, Current (Past 3 Months)
Binge-eating disorder, Current (Past 3 Months)
Generalized anxiety disorder, Current (Past 6 Months)
Medical, organic, drug cause ruled out (No, Yes, Uncertain)
Antisocial personality disorder, Lifetime
Primary diagnosis (Major depressive episode,)

The specified Other reasons for MINI not done will be listed.

6.3.5. Inventory of Depressive Symptomatology (Clinician-Rated)

The 30 item Inventory of Depressive Symptomatology clinician rated (IDS-C30) is designed to assess the severity of depressive symptoms. Each item is interval scaled from 0 to 3; 0 indicates absence of the symptom during the last 7 days. The IDS-C30 is scored by summing responses to 28 of the 30 items to obtain a total score ranging from 0 to 84. Either appetite increase or decrease, but not both, are used to calculate the total score. Weight increase or decrease, but not both, are used to calculate the total score.

The following variables will be summarized for the IDS-C30 performed at screening by intervention group:

Continuous Variables	Summary Type	
IDS-C30 total score	Descriptive statistics (N, mean, standard deviation [SD], median and range [minimum and maximum]	
Categorical Variables		
Was the questionnaire completed (Yes, No)	Frequency distribution with the number and	
Reason Not Done (Subject too ill, Subject refused, Other)	percentage of participants in each category.	

The specified Other reasons for IDC-C30 not done will be listed.

6.3.6. Psychotherapy

The following variables will be summarized for the investigator discussion with the participant regarding psychotherapy by intervention group:

Categorical Variables	Summary Type
Discussion of initiation/continuation of psychotherapy during study has taken place prior to randomization (Yes, No)	
Psychotherapy recommended based on pre-randomization discussion (Yes, No)	
Decision by the participant to follow the recommendation (prior to randomization) (Decision to follow recommendation, Decision to not follow recommendation)	
Psychotherapy started (Yes, No)	
Category of started psychotherapy (Cognitive–behavioral therapy, Nondirective supportive therapy, Behavioral activation therapy, Psychodynamic therapy, Systemic therapy, Problem-solving therapy, Interpersonal psychotherapy, Social skills training, Other)	Frequency distribution with the number and percentage of participants in each category.
Reason for starting (Patient's wish/preference, Suggested by treating physician, Suggested by third party, Unspecified - started prior the study, Other)	
Frequency (once, infrequent, as necessary, continue, daily, twice daily, three times daily, four times daily, every other day, weekly, twice weekly, three times weekly, four times	

weekly, every two weeks, every four weeks, monthly, twice per month, every three months, thrice, unknown, other)
Reason for stopping (Patient's decision, Lack of efficacy, Lack of tolerability, Lack of cooperation, Other)
Reason for change to another psychotherapeutic intervention (Suggested by the therapist, Lack of efficacy, Lack of tolerability, Lack of cooperation, Other)
Participant's adherence to psychotherapeutic intervention (Good, Moderate, Bad)

The other specifications for psychotherapy, reason for starting, reason for stopping and reason for change to another psychotherapeutic intervention will be listed.

6.3.7. Urine screen for drugs of abuse

The following variables will be summarized for the Urine screen for drugs of abuse performed at screening by intervention group:

Categorical Variables	Summary Type	
Was the sample collected (Yes, No)		
Amphetamine (Positive, Negative)		
Barbiturate (Positive, Negative)		
Cannabinoids (Positive, Negative)		
Cocaine (Positive, Negative)	Frequency distribution with the number and percentage of participants in each category.	
Methadone (Positive, Negative)		
Methamphetamine (Positive, Negative)		
Opiate (Positive, Negative)]	
Phencyclidine (Positive, Negative)		

6.3.8. Preplanned surgeries/procedures

The following variables will be summarized for preplanned surgeries/procedures by intervention group:

Categorical Variables	Summary Type
Are there any planned/scheduled surgeries/procedures which require hospitalization during the course of this trial (Yes, No)	
Allergic/Immunologic (ongoing yes / no)	Frequency distribution with the number and percentage of participants in each category.
Cardiovascular (ongoing yes / no)	
Dermatologic (ongoing yes / no)	
Ears, Nose and Throat/ (ongoing yes / no)	
Endocrine and Metabolic (ongoing yes / no)	
Eyes (ongoing yes / no)	

Gastrointestinal (ongoing yes / no)
Genito-urinary (ongoing yes / no)
Hematopoietic/Lymphatic (ongoing yes / no)
Musculoskeletal (ongoing yes / no)
Neurologic (ongoing yes / no)
Psychiatric (ongoing yes / no)
Reproductive/Breast (ongoing yes / no)
Respiratory (ongoing yes / no)
Other (ongoing yes / no)
Indication (Medical History, Prophylaxis, Other)

Details of surgery/procedure and associated medical history/prophylaxis/other will be listed.

6.4. Appendix 4 Major Protocol Deviations

In general, major protocol deviations may have the potential to impact participants' rights, safety or well-being, or the integrity and/or result of the clinical study. Participants with major protocol deviations will be identified prior to database lock. See the study specific Major Protocol Deviation Criteria document.

The participants with major protocol deviations will be summarized by category ("Protocol Deviation Coded Term)". Major protocol deviations will be listed presenting the coded term and the description ("PD criterion").

6.5. Appendix 5 Prior and Concomitant Medications

Prior and Concomitant medications will be coded using the World Health Organization Drug Dictionary (WHO-DD). Prior medications are defined as any therapy used before the day of first dose (partial or complete) of study intervention. Concomitant medications are defined as any therapy used on or after the same day as the first dose of study intervention, including those that started before and continue after the first dose of study intervention.

Summaries of concomitant medications will be presented by ATC term and study intervention. The proportion of participants who receive each concomitant medication will be summarized as well as the proportion of participants who receive at least 1 concomitant medication. In addition, concomitant medications of special interest will be presented as administered before the study intervention and during the study. These include benzodiazepines and sleeping medications. See Appendix 9 for specifications of the medications.

The indication of the concomitant medications will be summarized by study intervention. The associated adverse events or medical histories will be summarized.

Note: the SSRI/SNRI continued during the study in combination with the study drug is summarized separately. See section 5.7.1.

Prior medications, meaning the retrospective treatment failures, will be summarized by substance class, substance name and study intervention. The number of treatment failures will be summarized by study intervention.

6.6. Appendix 6 Medical History

The following variables will be summarized for subjects who experienced any past and/ or concomitant diseases at screening by intervention group:

Categorical Variables	Summary Type
Allergic/Immunologic (ongoing yes / no)	
Cardiovascular (ongoing yes / no)	
Dermatologic (ongoing yes / no)	
Ears, Nose and Throat/ (ongoing yes / no)	
Endocrine and Metabolic (ongoing yes / no)	
Eyes (ongoing yes / no)	
Gastrointestinal (ongoing yes / no)	
Genito-urinary (ongoing yes / no)	Frequency distribution with the number and percentage of participants in each category.
Hematopoietic/Lymphatic (ongoing yes / no)	F
Musculoskeletal (ongoing yes / no)	
Neurologic (ongoing yes / no)	
Psychiatric (ongoing yes / no)	
Reproductive/Breast (ongoing yes / no)	
Respiratory (ongoing yes / no)	
Other (ongoing yes / no)	

The verbatim term for the medical history condition/event will be listed.

6.7. Appendix 7 Intervention Compliance

Compliance calculation is not applicable for this study.

Relevant deviations from the dosing schedules will be documented through major protocol deviations. See the Major Protocol Deviation Criteria document for this study.

6.8. Appendix 8 Adverse Events of Special Interest

Adverse events of special interest are defined and grouped in the following MedDRA based categories as follows:

Sedation: sedation; somnolence; altered state of consciousness; depressed level of consciousness; hypersomnia; stupor

Dissociation: depersonalisation/derealisation disorder; derealisation; dissociative disorder; flashback; hallucination; hallucination, auditory; hallucination, visual; hallucination, illusion; somatic hallucination; hyperacusis; tinnitus; diplopia; vision blurred; ocular discomfort; photophobia; visual impairment; dysesthesia; oral dysesthesia; paraesthesia; paraesthesia oral; pharyngeal paraesthesia; time perception altered; daydreaming; delusional perception; feeling hot; feeling cold; feeling of body temperature change

Suicidality: completed suicide; depression suicidal; intentional overdose; intentional self-injury; multiple drug overdose intentional; poisoning deliberate; self-injurious behavior; self-injurious ideation; suicidal behavior; suicidal ideation; suicide attempt; toxicity to various agents

Suggestive of abuse potential: aggression; confusional state; decreased activity; dependence; disorientation; dissociation; dissociative disorder; dizziness; drug abuse; drug abuser; drug dependence; drug use disorder; drug detoxification; drug diversion; drug rehabilitation; drug tolerance; drug tolerance increased; drug withdrawal convulsions; drug withdrawal headache; drug withdrawal syndrome; euphoric mood; feeling abnormal; feeling drunk; feeling of relaxation; hallucination, auditory; hallucination, gustatory; hallucination, olfactory; hallucination, synesthetic; hallucination, tactile; hallucination, visual; hallucinations, mixed; inappropriate affect; mental impairment; product tampering; psychomotor hyperactivity; psychotic disorder; rebound effect; somatic hallucination; somnolence; substance abuser; substance use disorder; substance-induced mood disorder; substance-induced psychotic disorder; thinking abnormal; withdrawal arrhythmia; withdrawal syndrome

Cystitis: allergic cystitis; chemical cystitis; cystitis; cystitis erosive; cystitis hemorrhagic; cystitis interstitial; cystitis noninfective; cystitis ulcer active; cystitis-like symptom; pollakiuria; dysuria; micturition urgency; nocturia

Hepatic impairment: cholestasis and jaundice of hepatic origin; hepatic failure; fibrosis and cirrhosis; other liver damage-related conditions

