2.2.3.4. Safety Studies

As of 1 April 2019, the estimated cumulative number of participants exposed to esketamine in clinical trials (including healthy and special population [eg, renal and hepatic impairment but not with TRD or MDD] participants) was 2,955 (627 participants from Phase 1 program, 295 participants from Phase 2 program and approximately 2,033 participants from Phase 3 program). Key safety observations from this program are identified below.

- The safety profile of esketamine is well characterized and tolerable with manageable risks. Over the proposed therapeutic dose range for use in a TRD population (28 to 84 mg), most intervention-emergent adverse events (AEs) with esketamine occur shortly after dosing, when participants will be under the supervision of a health care professional, are transient, and resolve on the same day. Transient postdose symptoms were consistent with findings from the Phase 1 and 2a esketamine IV studies and were expected based on the pharmacologic profile. No new safety concerns associated with esketamine treatment were identified in Phase 2 and 3 studies.
- The most commonly observed adverse drug reactions in TRD patients treated with esketamine in combination with a newly initiated SSRI/SNRI in Phase 2 and Phase 3 studies (incidence ≥10% and greater than in the newly initiated SSRI/SNRI in combination with placebo group) were dissociation, dizziness, nausea, sedation, headache, vertigo, dysgeusia, hypoesthesia, anxiety, blood pressure increased, and vomiting.
- Several of the more common adverse effects of esketamine, including dissociative symptoms/perceptual changes, dizziness/vertigo, and anxiety, occurred on the day of dosing and resolved the same day. Dissociative symptoms/perceptual changes attenuated with continued treatment.
- The long-term safety profile of esketamine after continued treatment of up to 1 year was characterized in an uncontrolled, open-label study (TRD3004) of 802 participants (691 adults and 111 elderly [≥65 years of age]) with TRD. There were no new AEs reported with long-term repeated, intermittent weekly or every-other week dosing of esketamine (28, 56, or 84 mg) (following a 4-week induction phase of twice-weekly dosing) over a duration of up to 1 year.

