8.3.7. Adverse Events of Special Interest

Clinically relevant intervention-emergent AEs of special interest will be summarized separately, grouped in the following MedDRA based categories:

- Sedation: sedation; somnolence; altered state of consciousness; depressed level of consciousness; hypersomnia; stupor
- **Dissociation:** depersonalisation/derealisation disorder; derealisation; dissociative disorder; flashback; hallucination; hallucination, auditory; hallucination, visual; hallucination, illusion; somatic hallucination; hyperacusis; tinnitus; diplopia; vision blurred; ocular discomfort; photophobia; visual impairment; dysesthesia; oral dysesthesia; paraesthesia; paraesthesia oral; pharyngeal paraesthesia; time perception altered; daydreaming; delusional perception; feeling hot; feeling cold; feeling of body temperature change
- **Suicidality:** completed suicide; depression suicidal; intentional overdose; intentional self-injury; multiple drug overdose intentional; poisoning deliberate; self-injurious behavior; self-injurious ideation; suicidal behavior; suicidal ideation; suicide attempt; toxicity to various agents
- Suggestive of abuse potential: aggression; confusional state; decreased activity; dependence; disorientation; dissociation; dissociative disorder; dizziness; drug abuse; drug abuse; drug dependence; drug use disorder; drug detoxification; drug diversion; drug rehabilitation; drug tolerance; drug tolerance increased; drug withdrawal convulsions; drug withdrawal headache; drug withdrawal syndrome; euphoric mood; feeling abnormal; feeling drunk; feeling of relaxation; hallucination; hallucination, auditory; hallucination, gustatory; hallucination, olfactory: hallucination. synesthetic; hallucination, tactile: hallucination. visual: hallucinations, mixed; inappropriate affect; mental impairment; product tampering; psychomotor hyperactivity; psychotic disorder; rebound effect; somatic hallucination; somnolence; substance abuser; substance dependence; substance use; substance use disorder; substance-induced mood disorder; substance-induced psychotic disorder; thinking abnormal; withdrawal arrhythmia; withdrawal syndrome
- **Cystitis**: allergic cystitis; chemical cystitis; cystitis; cystitis erosive; cystitis hemorrhagic; cystitis interstitial; cystitis noninfective; cystitis ulcer active; cystitis-like symptom; pollakiuria; dysuria; micturition urgency; nocturia

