5.7.2. Adverse Events

The verbatim terms used in the CRF by investigators to identify adverse events will be coded using the Medical Dictionary for Regulatory Activities (MedDRA). All AEs and special reporting situations, whether serious or non-serious, will be reported from the time a signed and dated ICF is obtained until completion of the participant's 2-week safety follow-up visit. Serious AEs, including those spontaneously reported to the investigator within 30 days after the last dose of study intervention, must be reported.

Any AE occurring at or after the initial administration of study intervention through completion of the participant's 2-week safety follow-up visit is considered to be treatment emergent. Serious AEs reported within 30 days after the last dose of study intervention are also regarded as treatment emergent. If the event occurs on the day of the initial administration of study intervention, and either event time or time of administration are missing, then the event will be assumed to be treatment emergent. If the event date is recorded as partial or completely missing, then the event will be considered to be treatment emergent unless it is known to be prior to the first administration of study intervention based on partial onset date or resolution date. All reported treatmentemergent adverse events will be included in the analysis. For each adverse event, the number and percentage of participants who experience at least 1 occurrence of the given event will be summarized by intervention group.

Summary tables, for the first 8 weeks and for the whole study, will be provided for treatmentemergent adverse events:

- AEs
- Serious AEs (SAEs)
- AEs leading to discontinuation of each study agent within a study intervention
- AEs by severity

- AEs by relationship to each study agent within a study intervention
- AEs leading to dose interruption/dose modification of each study agent within a study intervention.

In addition to the summary tables, listings will be provided for participants who:

- Had SAEs
- Had AEs leading to discontinuation of study intervention.

Incidence of treatment-emergent adverse events of special interest will be summarized, grouped in the following MedDRA-based categories: sedation, dissociation, suicidality, suggestive of abuse potential, cystitis, and hepatic impairment. See Appendix 8 for a list of adverse events in each category.

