The number and percentage of participants taking concomitant medication for dissociation events (preferred term of Dissociation) at any time during each treatment phase will be provided.

A listing of participants who died will be provided.

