5.8.7. Definition of Subgroups

The following subgroups will be used to summarize parameters:

Subgroup	Variant	Definition
Sex	1	• Male
		• Female
Age Group	1	• Adult [18-64]
		• Elderly [>=65]
Number of previous	1	• 2
treatment failures		• >=3
Class of continued oral AD	1	SNRI
		• SSRI

The following parameters will be analyzed as described in the respective sections for the subgroups:

- Selected demographic and disease characteristics;
- The primary parameter and the major secondary parameter;
- MADRS;
- CGI-S and CGI-C;
- PHQ-9;
- QLDS;
- Selected AE parameters (including AEs of special interest).

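### The SAP's term list for the special-interest category Dissociation leaves out the preferred term Dissociation, so the category incidence is incomplete as written

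*SAP*

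**What the plan says.** SAP section 5.7.2 plans incidence summaries of treatment-emergent adverse events of special interest in six categories: sedation, dissociation, suicidality, suggestive of abuse potential, cystitis and hepatic impairment. For the content of each category it refers the analyst to an appendix: "See Appendix 8 for a list of adverse events in each category". That appendix (SAP section 6.8) opens the Dissociation entry with "Dissociation: depersonalisation/derealisation disorder; derealisation; dissociative disorder; flashback" and continues through hallucination, visual, sensory and temperature terms. Protocol section 8.3.7 starts its list the same way, "depersonalisation/derealisation disorder; derealisation; dissociative disorder; flashback", and gives the same terms throughout.

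The term Dissociation does occur elsewhere in the SAP:

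- In Appendix 8 it is listed under the abuse-potential category: "disorientation; dissociation; dissociative disorder; dizziness".
- Section 5.7.2 plans a summary of concomitant medication taken for "dissociation events (preferred term of Dissociation".

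Section 5.8.7 repeats the special-interest output by subgroup: "Selected AE parameters (including AEs of special interest".

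**The concern.** A category that defines a safety summary should contain the event it is named after. Here the list includes tinnitus, daydreaming and feeling hot, but not Dissociation. A programmer who builds the category flag from Appendix 8 would count a participant with tinnitus and miss a participant whose only event is Dissociation.

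Dissociation is also a characteristic esketamine effect. Protocol section 2.2.3.4 reports that the commonest reactions to esketamine in earlier studies, with incidence of at least 10% and above the placebo-combination group, "were dissociation, dizziness, nausea, sedation, headache, vertigo" and others. Missing events would therefore be expected mainly in the esketamine arm, which would make the sponsor's product look better on a prespecified safety category. A programmer might add the term informally, but that would be an undocumented departure from the SAP.

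**Working it through.** The plan states no figure on this point, so the check is one of list membership, followed by a reading of the surrounding text.

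**1. Membership.** Splitting the Appendix 8 lists at the semicolons gives:

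| Category (SAP Appendix 8) | Terms | Heading term listed? | Dissociation listed? |
|---|---|---|---|
| Sedation | 6 | yes | no |
| Dissociation | 27 | **no** | **no** |
| Cystitis | 13 | yes | no |
| Suggestive of abuse potential | not needed | not an event term | yes, once |

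The protocol 8.3.7 list for Dissociation has the same 27 terms.

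**2. Could another entry cover it?** The nearest is dissociative disorder. In the abuse-potential list of the same appendix, dissociation and dissociative disorder are adjacent but separate entries. The SAP therefore treats them as different terms.

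**3. Could the heading count as an implied member?** Sedation and Cystitis are the other two headings that are themselves plain event terms. Both are repeated as members of their own lists. The appendix therefore does not rely on the heading being understood as a term.

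**4. Is Dissociation a coded term in this trial?** Section 5.7.2 calls it a preferred term in the concomitant-medication summary. That summary is keyed to a term that the Dissociation category excludes.

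**5. Is it corrected elsewhere?** The SAP version history lists no change to the special-interest categories. Appendix 2, on changes to protocol-planned analyses, covers only the time-to-event methods ("since time to relapse is an exploratory endpoint, the analysis of this endpoint will only be descriptive").

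**6. Size.** Let D be the set of participants with an event coded to Dissociation, and L the set with at least one of the 27 listed terms.

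- Category incidence as written: P(L)
- Category incidence with the term added: P(L or D) = P(L) + P(D and not L)
- Undercount: P(D and not L), which lies between 0 and P(D)

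The undercount is zero if every participant with Dissociation also reports a listed term. It equals P(D) if none does. The documents give neither P(D) for this trial nor the overlap, so no number can be derived. The earlier-study figure of at least 10% is a lower limit on incidence in other trials and does not bound P(D and not L).

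**The case against.** The strongest reply is that little is lost. Every treatment-emergent event is tabulated for the first 8 weeks and for the whole study. Dissociation is counted under abuse potential, and a further summary is keyed to it by name. The special-interest tables are descriptive incidences with no planned test. All of this stands, and it limits the reach of the point to one grouped category and its subgroup repeats.

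The use of the 10% figure can also be challenged. Protocol 2.2.3.4 describes adverse drug reactions in studies with a newly initiated SSRI/SNRI, and it does not say whether dissociation there is the single preferred term or a grouped one. Overlap with listed terms such as derealisation, blurred vision and paraesthesia could be large. This is fair: the figure supports the likely direction of the error and nothing about its size.

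The term could have been lost when the PDF was read. The abuse-potential lists differ between the two documents: the SAP text lacks three terms that the protocol text has (hallucination on its own, substance dependence and substance use). An extraction loss cannot be fully excluded. It is unlikely, because the same term would have to vanish from the Dissociation list in both documents while surviving beside dissociative disorder in the abuse list of both.

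Appendix 8 can also be read loosely, since the hepatic entries describe groups of conditions and exclusion of Dissociation was plainly not intended. That explains how the slip arose. It does not change what the list says, and the Sedation and Cystitis entries count against a loose reading.

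Finally, the silence of Appendix 2 is no fault in itself, because the SAP list matches the protocol. It shows only that nothing there repairs the gap.

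**Conclusion.** The concern holds. As written, the Dissociation category excludes the event it is named after, and its incidence will be incomplete if Appendix 8 is followed. The two documents agree with each other, so this is a slip carried from the protocol into the SAP and not a conflict between them.

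The undercount cannot be computed. If Dissociation is again commoner with esketamine, the shortfall falls mainly in that arm. The conclusion assumes that the extracted lists are faithful and that the categories are programmed from Appendix 8 as section 5.7.2 directs. The point should be fixed. It is confined to one descriptive safety category and does not touch the primary or key secondary analysis.

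**What to change.** - Add the preferred term Dissociation to the Dissociation list in SAP Appendix 8.
- Record in SAP Appendix 2 that the list now differs from protocol section 8.3.7 by this term.
- Produce the special-interest tables, overall and by subgroup, from the corrected list.

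The cost is one term and one line of text, with no new data and no protocol amendment. The category incidence in each arm can only stay the same or rise.
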